	Moderate	xxx	xxx	xxx	xxx	xxx	xxx	xxx	xxx
	Severe	xxx	xxx	xxx	xxx	xxx	xxx	xxx	xxx
Visit 3-visit 4		Absent	xxx	xxx	xxx	xxx	xxx	xxx	xxx
	Absent	xxx	xxx	xxx	xxx	xxx	xxx	xxx	xxx
	Mild	xxx	xxx	xxx	xxx	xxx	xxx	xxx	xxx
	Moderate	xxx	xxx	xxx	xxx	xxx	xxx	xxx	xxx
	Severe	xxx	xxx	xxx	xxx	xxx	xxx	xxx	xxx
...									
continued...									

		LEO 90100 (n=xxx)				Vehicle (n=xxx)			
		End of relapse				End of relapse			
Physician's assessment of local safety and tolerability		Absent	Mild	Mod	Sev	Absent	Mild	Mod	Sev
Visit									
Visit 14-visit 15									
Absent		xxx	xxx	xxx	xxx	xxx	xxx	xxx	xxx
Mild		xxx	xxx	xxx	xxx	xxx	xxx	xxx	xxx
Moderate		xxx	xxx	xxx	xxx	xxx	xxx	xxx	xxx
Severe		xxx	xxx	xxx	xxx	xxx	xxx	xxx	xxx
Total									
Absent		xxx	xxx	xxx	xxx	xxx	xxx	xxx	xxx
Mild		xxx	xxx	xxx	xxx	xxx	xxx	xxx	xxx
Moderate		xxx	xxx	xxx	xxx	xxx	xxx	xxx	xxx
Severe		xxx	xxx	xxx	xxx	xxx	xxx	xxx	xxx
Perilesional oedema									
<as above>									
Perilesional dryness									
<as above>									
Perilesional erosion									
<as above>									

Mod: Moderate, Sev: Severe

Shell 74: Subject's assessment of local safety and tolerability by visit in open-label phase: open-label safety analysis set

Subject's assessment of local safety and tolerability	Visit	All subjects in open-label safety analysis set (n=xxx)	Randomised subjects (n=xxx)	Not randomised subjects (n=xxx)	
Application site burning or pain					
Visit 1					
Number of subjects		xxx	xxx	xxx	
Absent		xxx (xx.x%)	xxx (xx.x%)	xxx (xx.x%)	
Mild		xxx (xx.x%)	xxx (xx.x%)	xxx (xx.x%)	
Moderate		xxx (xx.x%)	xxx (xx.x%)	xxx (xx.x%)	
Severe		xxx (xx.x%)	xxx (xx.x%)	xxx (xx.x%)	
Visit 2					
<as above>					

Shell 75: Shift table for subject's assessment of local safety and tolerability from start to end of open-label phase: open-label safety analysis set

Visit	Subject's assessment of local safety and tolerability	All subjects in open-label safety analysis set (n=xxx)				Randomised subjects (n=xxx)				Not randomised subjects (n=xxx)			
		Visit 2				Visit 2				Visit 2			
		Absent	Mild	Mod	Sev	Absent	Mild	Mod	Sev	Absent	Mild	Mod	Sev
Visit 1													
Application site burning or pain													
Absent		XXX	XXX	XXX	XXX	XXX	XXX	XXX	XXX	XXX	XXX	XXX	XXX
Mild		XXX	XXX	XXX	XXX	XXX	XXX	XXX	XXX	XXX	XXX	XXX	XXX
Moderate		XXX	XXX	XXX	XXX	XXX	XXX	XXX	XXX	XXX	XXX	XXX	XXX
Severe		XXX	XXX	XXX	XXX	XXX	XXX	XXX	XXX	XXX	XXX	XXX	XXX

Mod: Moderate, Sev: Severe

Shell 76: Subject's assessment of local safety and tolerability by visit not related to relapse: safety analysis set

Subject's assessment of local safety and tolerability	LEO 90100 (n=xxx)	Vehicle (n=xxx)
Application site burning or pain		
Visit 2		
Number of subjects	xxx	xxx
Absent	xxx (xx.x%)	xxx (xx.x%)
Mild	xxx (xx.x%)	xxx (xx.x%)
Moderate	xxx (xx.x%)	xxx (xx.x%)
Severe	xxx (xx.x%)	xxx (xx.x%)
...		
Visit 15		
<as above>		

**Shell 77: Subject's assessment of local safety and tolerability by visit for start of relapse:
safety analysis set**

Subject's assessment of local safety and tolerability		LEO 90100	Vehicle
Visit		(n=xxx)	(n=xxx)
Application site burning or pain			
Visit 2-visit 3			
Number of subjects		xxx	xxx
Absent		xxx (xx.x%)	xxx (xx.x%)
Mild		xxx (xx.x%)	xxx (xx.x%)
Moderate		xxx (xx.x%)	xxx (xx.x%)
Severe		xxx (xx.x%)	xxx (xx.x%)
Visit 3			
<as above>			
Visit 3-4			
<as above>			
Visit 4			
<as above>			
...			
Visit 14-visit 15			
<as above>			
Total			
Number of relapses		xxx	xxx
Number of subjects		xxx	xxx
Absent		xxx (xx.x%)	xxx (xx.x%)
Mild		xxx (xx.x%)	xxx (xx.x%)
Moderate		xxx (xx.x%)	xxx (xx.x%)
Severe		xxx (xx.x%)	xxx (xx.x%)

**Shell 78: Subject's assessment of local safety and tolerability by visit for end of relapse:
safety analysis set**

Subject's assessment of local safety and tolerability	Visit	LEO 90100 (n=xxx)	Vehicle (n=xxx)
Application site burning or pain			
Visit 3-visit 4			
Number of subjects		xxx	xxx
Absent		xxx (xx.x%)	xxx (xx.x%)
Mild		xxx (xx.x%)	xxx (xx.x%)
Moderate		xxx (xx.x%)	xxx (xx.x%)
Severe		xxx (xx.x%)	xxx (xx.x%)
Visit 4			
<as above>			
Visit 4-5			
<as above>			
...			
Visit 15			
<as above>			
Visit 15-UNS¹			
<as above>			
Total			
Number of relapses		xxx	xxx
Number of subjects		xxx	xxx
Absent		xxx (xx.x%)	xxx (xx.x%)
Mild		xxx (xx.x%)	xxx (xx.x%)
Moderate		xxx (xx.x%)	xxx (xx.x%)
Severe		xxx (xx.x%)	xxx (xx.x%)

1) Possible unscheduled visits (UNS) after visit 15 in the maintenance phase.

Shell 79; Shift table for subject's assessment of local safety and tolerability from start of relapse to end of relapse by visit for start of relapse: safety analysis set

		LEO 90100 (n=xxx)				Vehicle (n=xxx)			
Subject's assessment of local safety and tolerability		End of relapse				End of relapse			
Visit	Absent	Mild	Mod	Sev	Absent	Mild	Mod	Sev	
Application site burning or pain									
Visit 2-visit 3									
Absent	xxx	xxx	xxx	xxx	xxx	xxx	xxx	xxx	xxx
Mild	xxx	xxx	xxx	xxx	xxx	xxx	xxx	xxx	xxx
Moderate	xxx	xxx	xxx	xxx	xxx	xxx	xxx	xxx	xxx
Severe	xxx	xxx	xxx	xxx	xxx	xxx	xxx	xxx	xxx
Visit 3									
Absent	xxx	xxx	xxx	xxx	xxx	xxx	xxx	xxx	xxx
Mild	xxx	xxx	xxx	xxx	xxx	xxx	xxx	xxx	xxx
Moderate	xxx	xxx	xxx	xxx	xxx	xxx	xxx	xxx	xxx
Severe	xxx	xxx	xxx	xxx	xxx	xxx	xxx	xxx	xxx
Visit 3-visit 4									
Absent									
Mild									
Moderate									
Severe									
...									
Visit 14-visit 15									
Absent	xxx	xxx	xxx	xxx	xxx	xxx	xxx	xxx	xxx
Mild	xxx	xxx	xxx	xxx	xxx	xxx	xxx	xxx	xxx
Moderate	xxx	xxx	xxx	xxx	xxx	xxx	xxx	xxx	xxx
Severe	xxx	xxx	xxx	xxx	xxx	xxx	xxx	xxx	xxx

continued...

Subject's assessment of local safety and tolerability					Vehicle			
Visit	End of relapse				End of relapse			
	Absent	Mild	Mod	Sev	Absent	Mild	Mod	Sev
Total					xxx	xxx	xxx	xxx
Absent	xxx	xxx	xxx	xxx	xxx	xxx	xxx	xxx
Mild	xxx	xxx	xxx	xxx	xxx	xxx	xxx	xxx
Moderate	xxx	xxx	xxx	xxx	xxx	xxx	xxx	xxx
Severe	xxx	xxx	xxx	xxx	xxx	xxx	xxx	xxx

Mod: Moderate, Sev: Severe

Shell 80: Change in vital signs from baseline to end of open-label phase: open-label safety analysis set

Vital sign Change	Open-label LEO 90100 (n=xxx)
Parameter 1 (<unit>)	
Number of subjects	xxx
Mean (SD)	xx.x (xx.x)
Median	xx.x
Q1;Q3	xx.x;xx.x
Min;Max	xx.x;xx.x
Parameter 2 (<unit>)	
Number of subjects	xxx
Mean (SD)	xx.x (xx.x)
Median	xx.x
Q1;Q3	xx.x;xx.x
Min;Max	xx.x;xx.x
...	
Parameter k (<unit>)	
Number of subjects	xxx
Mean (SD)	xx.x (xx.x)
Median	xx.x
Q1;Q3	xx.x;xx.x
Min;Max	xx.x;xx.x

SD: Standard deviation, Q1: 1st quartile, Q3: 3rd quartile.

Shell 81: Change in vital signs from randomisation to end of maintenance phase <for subjects XXX>: safety analysis set

Vital sign Change	LEO 90100 (n=xxx)	Vehicle (n=xxx)
<Parameter 1> (<unit>)		
Number of subjects	xxx	xxx
Mean (SD)	xx.x (xx.x)	xx.x (xx.x)
Median	xx.x	xx.x
Q1;Q3	xx.x;xx.x	xx.x;xx.x
Min;Max	xx.x;xx.x	xx.x;xx.x
<Parameter 2> (<unit>)		
Number of subjects	xxx	xxx
Mean (SD)	xx.x (xx.x)	xx.x (xx.x)
Median	xx.x	xx.x
Q1;Q3	xx.x;xx.x	xx.x;xx.x
Min;Max	xx.x;xx.x	xx.x;xx.x
...		
<Parameter k> (<unit>)		
Number of subjects	xxx	xxx
Mean (SD)	xx.x (xx.x)	xx.x (xx.x)
Median	xx.x	xx.x
Q1;Q3	xx.x;xx.x	xx.x;xx.x
Min;Max	xx.x;xx.x	xx.x;xx.x

SD: Standard deviation, Q1: 1st quartile, Q3: 3rd quartile.

**Shell 82: Change in laboratory parameters from baseline to end of open-label phase:
open-label safety analysis set**

Laboratory assessment	Open-label LEO 90100
Laboratory parameter	(n=xxx)
Change	
Biochemistry	
<Parameter 1> (<unit>)	
Number of subjects	xxx
Mean (SD)	x.xx (x.xx)
Median	x.xx
Q1;Q3	x.xx; x.xx
Min;Max	x.xx; x.xx
<Parameter 2> (<unit>)	
Number of subjects	xxx
Mean (SD)	x.xx (x.xx)
Median	x.xx
Q1;Q3	x.xx; x.xx
Min;Max	x.xx; x.xx
...	
Urinalysis	
<Parameter 1> (<unit>)	
Number of subjects	xxx
Mean (SD)	x.xx (x.xx)
Median	x.xx
Q1;Q3	x.xx; x.xx
Min;Max	x.xx; x.xx
<Parameter 2> (<unit>)	
Number of subjects	xxx
Mean (SD)	x.xx (x.xx)
Median	x.xx
Q1;Q3	x.xx; x.xx
Min;Max	x.xx; x.xx
...	

SD: Standard deviation, Q1: 1st quartile, Q3: 3rd quartile.

Shell 83: Change in laboratory parameters from randomisation to end of maintenance phase <for subjects XXX>: safety analysis set

Laboratory assessment	LEO 90100	Vehicle
Laboratory parameter	(n=xxx)	(n=xxx)
Change		
Biochemistry		
<Parameter 1> (<unit>)		
Number of subjects	xxx	xxx
Mean (SD)	xx.x (xx.x)	xx.x (xx.x)
Median	xx.x	xx.x
Q1;Q3	xx.x;xx.x	xx.x;xx.x
Min;Max	xx.x;xx.x	xx.x;xx.x
<Parameter 2> (<unit>)		
Number of subjects	xxx	xxx
Mean (SD)	xx.x (xx.x)	xx.x (xx.x)
Median	xx.x	xx.x
Q1;Q3	xx.x;xx.x	xx.x;xx.x
Min;Max	xx.x;xx.x	xx.x;xx.x
...		
Urinalysis		
<Parameter 1> (<unit>)		
Number of subjects	xxx	xxx
Mean (SD)	xx.x (xx.x)	xx.x (xx.x)
Median	xx.x	xx.x
Q1;Q3	xx.x;xx.x	xx.x;xx.x
Min;Max	xx.x;xx.x	xx.x;xx.x
<Parameter 2> (<unit>)		
Number of subjects	xxx	xxx
Mean (SD)	xx.x (xx.x)	xx.x (xx.x)
Median	xx.x	xx.x
Q1;Q3	xx.x;xx.x	xx.x;xx.x
Min;Max	xx.x;xx.x	xx.x;xx.x
...		

SD: Standard deviation, Q1: 1st quartile, Q3: 3rd quartile.

Shell 84: Shift table for laboratory parameter categories at baseline against end of open-label phase: open-label safety analysis set

Open-label LEO 90100 (n=xxx) End of open-label phase				
Laboratory assessment Laboratory parameter	Low	Normal	High	Missing
Biochemistry				
<Parameter 1>	xx	xx	xx	xx
Baseline Low	xx	xx	xx	xx
Baseline Normal	xx	xx	xx	xx
Baseline High	xx	xx	xx	xx
Baseline Missing				
<Parameter 2>				
...				
Urinalysis				
<Parameter 1>	xx	xx	xx	xx
Baseline Low	xx	xx	xx	xx
Baseline Normal	xx	xx	xx	xx
Baseline High	xx	xx	xx	xx
Baseline Missing				
<Parameter 2>				
...				

Shell 85: Shift table for laboratory parameter categories at randomisation against end of maintenance phase <for subjects XXX>: safety analysis set

Laboratory assessment Laboratory parameter	LEO 90100 (n=xxx)				Vehicle (n=xxx)			
	End of maintenance phase				End of maintenance phase			
	Low	Normal	High	Missing	Low	Normal	High	Missing
Biochemistry								
<Parameter 1>								
Randomisation Low	xx	xx	xx	xx	xx	xx	xx	xx
Randomisation Normal	xx	xx	xx	xx	xx	xx	xx	xx
Randomisation High	xx	xx	xx	xx	xx	xx	xx	xx
Randomisation Missing	xx	xx	xx	xx	xx	xx	xx	xx
<Parameter 2>								
...								
Urinalysis								
<Parameter 1>								
Randomisation Low	xx	xx	xx	xx	xx	xx	xx	xx
Randomisation Normal	xx	xx	xx	xx	xx	xx	xx	xx
Randomisation High	xx	xx	xx	xx	xx	xx	xx	xx
Randomisation Missing	xx	xx	xx	xx	xx	xx	xx	xx
<Parameter 2>								
...								

Shell 86: Compliance with treatment instructions during open-label treatment phase: open-label safety analysis

Open-label LEO 90100 (n=xxx)	
Number of subjects in non-compliance with treatment instructions	xxx (xx.x)
Number of daily IMP applications missed	xxx (xx.x)
Percentage of missed daily IMP applications:	
>0% and <=10%	xx (xx.x)
>10% and <=20%	xx (xx.x)
>20% and <=30%	xx (xx.x)
>30%	xx (xx.x)

Shell 87: Compliance with treatment instructions during maintenance phase excluding periods of treatment with rescue medication: maintenance phase safety analysis set

	LEO 90100 (n=xxx)	Vehicle (n=xxx)
Total maintenance phase		
Number of subjects in non-compliance with treatment instructions	xxx (xx.x)	xxx (xx.x)
Percentage of weeks in non-compliance with treatment instructions:		
>0% and <=10%	xx (xx.x)	xx (xx.x)
>10% and <=20%	xx (xx.x)	xx (xx.x)
>20% and <=30%	xx (xx.x)	xx (xx.x)
>30%	xx (xx.x)	xx (xx.x)
Visit 2 - visit 3		
Number of subjects	xxx	xxx
Number of subjects in non-compliance with treatment instructions	xxx (xx.x)	xxx (xx.x)
...		
Visit 14 - visit 15		
Number of subjects	xxx	xxx
Number of subjects in non-compliance with treatment instructions	xxx (xx.x)	xxx (xx.x)

Shell 88: Compliance with treatment instructions during periods of treatment with rescue medication: maintenance phase safety analysis set

	LEO 90100 (n=xxx)	Vehicle (n=xxx)
No of daily IMP applications missed	xx (xx.x)	xx (xx.x)
Percentage of missed daily IMP applications:		
>0% and <=10%	xx (xx.x)	xx (xx.x)
>10% and <=20%	xx (xx.x)	xx (xx.x)
>20% and <=30%	xx (xx.x)	xx (xx.x)
>30%	xx (xx.x)	xx (xx.x)

Trial ID: LP0053-1004	Date: 15-JUL-2019	Version: 1.0 Page 165 of 177
-----------------------	-------------------	---------------------------------

Shell 89: Duration of exposure during the open-label treatment phase: open-label safety analysis set

Open-label LEO 90100 (n=xxx)	
Duration of exposure	
Number of days	xxx
Mean (SD)	xx.x (xx.x)
Median	xx.x
Q1;Q3	xx.x;xx.x
Min;Max	xx.x;xx.x

SD: Standard deviation, Q1: 1st quartile, Q3: 3rd quartile.

Shell 90: Duration of exposure during the maintenance phase: safety analysis set

LEO 90100 (n=xxx)	Vehicle (n=xxx)
Duration of exposure	
Number of days	xxx
Mean (SD)	xx.x (xx.x)
Median	xx.x
Q1;Q3	xx.x;xx.x
Min;Max	xx.x;xx.x

SD: Standard deviation, Q1: 1st quartile, Q3: 3rd quartile.

Shell 91: Amount of investigational medicinal product used during open-label treatment phase: open-label safety analysis set

Open-label LEO 90100 (n=xxx)	
Amount of IMP used	
Number of subjects	xxx
Mean (SD)	xx.x (xx.x)
Median	xx.x
Q1;Q3	xx.x;xx.x
Min;Max	xx.x;xx.x

SD: Standard deviation, Q1: 1st quartile, Q3: 3rd quartile.

The amount of IMP used is normalised by the number of days in the open-label phase for each subject.

Trial ID: **LP0053-1004**

Date: **15-JUL-2019**

Version: 1.0

Page 166 of 177

Shell 92: Amount of investigational medicinal product used during maintenance phase: safety analysis set

	LEO 90100 (n=xxx)		Vehicle (n=xxx)	
	Total IMP	Rescue IMP	Total IMP	Rescue IMP
Number of subjects	xxx	xxx	xxx	xxx
Mean (SD)	xx.x (xx.x)	xx.x (xx.x)	xx.x (xx.x)	xx.x (xx.x)
Median	xx.x	xx.x	xx.x	xx.x
Q1;Q3	xx.x;xx.x	xx.x;xx.x	xx.x;xx.x	xx.x;xx.x
Min;Max	xx.x;xx.x	xx.x;xx.x	xx.x;xx.x	xx.x;xx.x

SD: Standard deviation, Q1: 1st quartile, Q3: 3rd quartile.

The amount of IMP used for each subject is normalised by the number of days in the maintenance phase or number of days in remission, respectively.

Shell 93: Cumulative amount of investigational medical product used up to scheduled visits: maintenance phase safety analysis set

	LEO 90100 (n=xxx)	Vehicle (n=xxx)
Visit 3		
Number of subjects	xxx	xxx
Mean (SD)	xx.x (xx.x)	xx.x (xx.x)
Median	xx.x	xx.x
Q1;Q3	xx.x;xx.x	xx.x;xx.x
Min;Max	xx.x;xx.x	xx.x;xx.x
...		
Visit 15		
Number of subjects	xxx	xxx
Mean (SD)	xx.x (xx.x)	xx.x (xx.x)
Median	xx.x	xx.x
Q1;Q3	xx.x;xx.x	xx.x;xx.x
Min;Max	xx.x;xx.x	xx.x;xx.x

SD: Standard deviation, Q1: 1st quartile, Q3: 3rd quartile.

Shell 94: Serum-cortisol concentration at time 0 and at 30 and at 60 minutes after ACTH-challenge test by visit: open-label HPA analysis set

Open-label LEO 90100 (n=xxx)	
Visit 1	
0 min (before ACTH-challenge test)	
Number of subjects	xxx
Mean (SD)	xx.x (xx.x)
Median	xx.x
Q1;Q3	xx.x;xx.x
Min;Max	xx.x;xx.x
30 min after ACTH-challenge test	
Number of subjects	xxx
Mean (SD)	xx.x (xx.x)
Median	xx.x
Q1;Q3	xx.x;xx.x
Min;Max	xx.x;xx.x
60 min after ACTH-challenge test	
Number of subjects	xxx
Mean (SD)	xx.x (xx.x)
Median	xx.x
Q1;Q3	xx.x;xx.x
Min;Max	xx.x;xx.x
Visit 2	
0 min (before ACTH-challenge test)	
Number of subjects	xxx
Mean (SD)	xx.x (xx.x)
Median	xx.x
Q1;Q3	xx.x;xx.x
Min;Max	xx.x;xx.x
30 min after ACTH-challenge test	
Number of subjects	xxx
Mean (SD)	xx.x (xx.x)
Median	xx.x
Q1;Q3	xx.x;xx.x
Min;Max	xx.x;xx.x
60 min after ACTH-challenge test	
Number of subjects	xxx
Mean (SD)	xx.x (xx.x)
Median	xx.x
Q1;Q3	xx.x;xx.x
Min;Max	xx.x;xx.x

Shell 95: Individual data for subjects with serum cortisol concentration ≤ 18 mcg/dL at either 30 minutes or 60 minutes after ACTH-challenge: open-label HPA analysis set.

Subject	Visit	Sample time	Serum cortisol concentration (mcg/dL)	Change in serum cortisol concentration from time 0 (mcg/dL)	BSA (%)
<subject id>	Visit xx	0 min	xx.x		xx.x
		30 min	xx.x	xx.x	
		60 min	xx.x	xx.x	
	Visit xx	0 min	xx.x		xx.x
		30 min	xx.x	xx.x	
		60 min	xx.x	xx.x	
	...				
<subject id>	Visit xx	0 min	xx.x		xx.x
		30 min	xx.x	xx.x	
		60 min	xx.x	xx.x	
	Visit xx	0 min	xx.x		xx.x
		30 min	xx.x	xx.x	
		60 min	xx.x	xx.x	
	...				

Shell 96: Subjects with serum cortisol concentration ≤ 18 mcg/dL at both 30 and 60 minutes after ACTH-challenge in open-label phase; open-label HPA analysis set

		Open-label LEO 90100 (n=xxx)
Visit	Serum Cortisol Concentration (mcg/dL)	Number of subjects (%)
Visit 1		
30 min after ACTH challenge test		
	≤ 18 mcg/dL	xx (xx.x)
	>18 mcg/dL	xx (xx.x)
	Total	xx (xx.x)
60 min after ACTH challenge test		
	≤ 18 mcg/dL	xx (xx.x)
	>18 mcg/dL	xx (xx.x)
	Total	xx (xx.x)
30 and 60 min after ACTH challenge test		
	≤ 18 mcg/dL	xx (xx.x)
	>18 mcg/dL	xx (xx.x)
	Total	xx (xx.x)
Visit 2		
30 min after ACTH challenge test		
	≤ 18 mcg/dL	xx (xx.x)
	>18 mcg/dL	xx (xx.x)
	Total	xx (xx.x)
60 min after ACTH challenge test		
	≤ 18 mcg/dL	xx (xx.x)
	>18 mcg/dL	xx (xx.x)
	Total	xx (xx.x)
30 and 60 min after ACTH challenge test		
	≤ 18 mcg/dL	xx (xx.x)
	>18 mcg/dL	xx (xx.x)
	Total	xx (xx.x)

Shell 97: Serum-cortisol concentration at time 0 and at 30 and at 60 minutes after ACTH-challenge test by visit: HPA analysis set

	All randomised subjects in the HPA axis group (n=xxx)	LEO 90100 (n=xxx)	Vehicle (n=xxx)
Visit 2			
0 min (before ACTH-challenge test)			
Number of subjects	xxx	xxx	xxx
Mean (SD)	xx.x (xx.x)	xx.x (xx.x)	xx.x (xx.x)
Median	xx.x	xx.x	xx.x
Q1;Q3	xx.x;xx.x	xx.x;xx.x	xx.x;xx.x
Min;Max	xx.x;xx.x	xx.x;xx.x	xx.x;xx.x
30 min after ACTH-challenge test			
Number of subjects	xxx	xxx	xxx
Mean (SD)	xx.x (xx.x)	xx.x (xx.x)	xx.x (xx.x)
Median	xx.x	xx.x	xx.x
Q1;Q3	xx.x;xx.x	xx.x;xx.x	xx.x;xx.x
Min;Max	xx.x;xx.x	xx.x;xx.x	xx.x;xx.x
60 min after ACTH-challenge test			
Number of subjects	xxx	xxx	xxx
Mean (SD)	xx.x (xx.x)	xx.x (xx.x)	xx.x (xx.x)
Median	xx.x	xx.x	xx.x
Q1;Q3	xx.x;xx.x	xx.x;xx.x	xx.x;xx.x
Min;Max	xx.x;xx.x	xx.x;xx.x	xx.x;xx.x
Visit 8			
0 min (before ACTH-challenge test)			
Number of subjects	xxx	xxx	xxx
Mean (SD)	xx.x (xx.x)	xx.x (xx.x)	xx.x (xx.x)
Median	xx.x	xx.x	xx.x
Q1;Q3	xx.x;xx.x	xx.x;xx.x	xx.x;xx.x
Min;Max	xx.x;xx.x	xx.x;xx.x	xx.x;xx.x
30 min after ACTH-challenge test			
Number of subjects	xxx	xxx	xxx
Mean (SD)	xx.x (xx.x)	xx.x (xx.x)	xx.x (xx.x)
Median	xx.x	xx.x	xx.x
Q1;Q3	xx.x;xx.x	xx.x;xx.x	xx.x;xx.x
Min;Max	xx.x;xx.x	xx.x;xx.x	xx.x;xx.x
60 min after ACTH-challenge test			
Number of subjects	xxx	xxx	xxx
Mean (SD)	xx.x (xx.x)	xx.x (xx.x)	xx.x (xx.x)
Median	xx.x	xx.x	xx.x
Q1;Q3	xx.x;xx.x	xx.x;xx.x	xx.x;xx.x
Min;Max	xx.x;xx.x	xx.x;xx.x	xx.x;xx.x

continued...

All randomised subjects in the HPA axis group (n=xxx)	LEO 90100 (n=xxx)	Vehicle (n=xxx)
Visit 15		
0 min (before ACTH-challenge test)		
Number of subjects		
Mean (SD)		
Median		
Q1;Q3		
Min;Max		
30 min after ACTH-challenge test		
Number of subjects		
Mean (SD)		
Median		
Q1;Q3		
Min;Max		
60 min after ACTH-challenge test		
Number of subjects		
Mean (SD)		
Median		
Q1;Q3		
Min;Max		

Shell 98: Subjects with serum cortisol concentration ≤ 18 mcg/dL at both 30 and 60 minutes after ACTH-challenge in maintenance phase; HPA analysis set

		All randomised subjects in the HPA axis group (n=xxx)		LEO 90100 (n=xxx)	Vehicle (n=xxx)
Visit	Serum Cortisol Concentration (mcg/dL)	Number of subjects (%)	Number of subjects (%)	Number of subjects (%)	
Visit 2					
	30 min after ACTH challenge test				
	≤ 18 mcg/dL	xx (xx.x)	xx (xx.x)	xx (xx.x)	xx (xx.x)
	>18 mcg/dL	xx (xx.x)	xx (xx.x)	xx (xx.x)	xx (xx.x)
	Total	xx (xx.x)	xx (xx.x)	xx (xx.x)	xx (xx.x)
	60 min after ACTH challenge test				
	≤ 18 mcg/dL	xx (xx.x)	xx (xx.x)	xx (xx.x)	xx (xx.x)
	>18 mcg/dL	xx (xx.x)	xx (xx.x)	xx (xx.x)	xx (xx.x)
	Total	xx (xx.x)	xx (xx.x)	xx (xx.x)	xx (xx.x)
	30 and 60 min after ACTH challenge test				
	≤ 18 mcg/dL	xx (xx.x)	xx (xx.x)	xx (xx.x)	xx (xx.x)
	>18 mcg/dL	xx (xx.x)	xx (xx.x)	xx (xx.x)	xx (xx.x)
	Total	xx (xx.x)	xx (xx.x)	xx (xx.x)	xx (xx.x)
Visit 8					
	30 min after ACTH challenge test				
	≤ 18 mcg/dL	xx (xx.x)	xx (xx.x)	xx (xx.x)	xx (xx.x)
	>18 mcg/dL	xx (xx.x)	xx (xx.x)	xx (xx.x)	xx (xx.x)
	Total	xx (xx.x)	xx (xx.x)	xx (xx.x)	xx (xx.x)
	60 min after ACTH challenge test				
	≤ 18 mcg/dL	xx (xx.x)	xx (xx.x)	xx (xx.x)	xx (xx.x)
	>18 mcg/dL	xx (xx.x)	xx (xx.x)	xx (xx.x)	xx (xx.x)
	Total	xx (xx.x)	xx (xx.x)	xx (xx.x)	xx (xx.x)
	30 and 60 min after ACTH challenge test				
	≤ 18 mcg/dL	xx (xx.x)	xx (xx.x)	xx (xx.x)	xx (xx.x)
	>18 mcg/dL	xx (xx.x)	xx (xx.x)	xx (xx.x)	xx (xx.x)
	Total	xx (xx.x)	xx (xx.x)	xx (xx.x)	xx (xx.x)

continued..

		All randomised subjects in the HPA axis group (n=xxx)	LEO 90100 (n=xxx)	Vehicle (n=xxx)
Visit	Serum Cortisol Concentration (mcg/dL)	Number of subjects (%)	Number of subjects (%)	Number of subjects (%)
Visit 15				
30 min after ACTH challenge test				
≤18 mcg/dL	xx (xx.x)	xx (xx.x)	xx (xx.x)	xx (xx.x)
>18 mcg/dL	xx (xx.x)	xx (xx.x)	xx (xx.x)	xx (xx.x)
Total	xx (xx.x)	xx (xx.x)	xx (xx.x)	xx (xx.x)
60 min after ACTH challenge test				
≤18 mcg/dL	xx (xx.x)	xx (xx.x)	xx (xx.x)	xx (xx.x)
>18 mcg/dL	xx (xx.x)	xx (xx.x)	xx (xx.x)	xx (xx.x)
Total	xx (xx.x)	xx (xx.x)	xx (xx.x)	xx (xx.x)
30 and 60 min after ACTH challenge test				
≤18 mcg/dL	xx (xx.x)	xx (xx.x)	xx (xx.x)	xx (xx.x)
>18 mcg/dL	xx (xx.x)	xx (xx.x)	xx (xx.x)	xx (xx.x)
Total	xx (xx.x)	xx (xx.x)	xx (xx.x)	xx (xx.x)

Shell 99: Individual data for subjects with serum cortisol concentration ≤ 18 mcg/dL at either 30 minutes or 60 minutes after ACTH-challenge: HPA analysis set.

Subject	Visit	Sample time	Serum cortisol concentration (mcg/dL)	Change in serum cortisol concentration from time 0 (mcg/dL)	BSA (%)
<subject id>	Visit xx	0 min	xx.x		xx.x
		30 min	xx.x	xx.x	
		60 min	xx.x	xx.x	
	Visit xx	0 min	xx.x		xx.x
		30 min	xx.x	xx.x	
		60 min	xx.x	xx.x	
	...				
<subject id>	Visit xx	0 min	xx.x		xx.x
		30 min	xx.x	xx.x	
		60 min	xx.x	xx.x	
	Visit xx	0 min	xx.x		xx.x
		30 min	xx.x	xx.x	
		60 min	xx.x	xx.x	
	...				

Shell 100: Serum-cortisol concentration at time 0 and at 30 and at 60 minutes after ACTH-challenge in the follow-up phase: HPA analysis set

	All randomised subjects in the HPA axis group (n=xxx)	LEO 90100 (n=xxx)	Vehicle (n=xxx)
Follow-up visit 2			
0 min (before ACTH-challenge test)			
Number of subjects	xxx	xxx	xxx
Mean (SD)	xx.x (xx.x)	xx.x (xx.x)	xx.x (xx.x)
Median	xx.x	xx.x	xx.x
Q1;Q3	xx.x;xx.x	xx.x;xx.x	xx.x;xx.x
Min;Max	xx.x;xx.x	xx.x;xx.x	xx.x;xx.x
30 min after ACTH-challenge test			
Number of subjects	xxx	xxx	xxx
Mean (SD)	xx.x (xx.x)	xx.x (xx.x)	xx.x (xx.x)
Median-	xx.x	xx.x	xx.x
Q1;Q3	xx.x;xx.x	xx.x;xx.x	xx.x;xx.x
Min;Max	xx.x;xx.x	xx.x;xx.x	xx.x;xx.x
60 min after ACTH-challenge test			
Number of subjects	xxx	xxx	xxx
Mean (SD)	xx.x (xx.x)	xx.x (xx.x)	xx.x (xx.x)
Median	xx.x	xx.x	xx.x
Q1;Q3	xx.x;xx.x	xx.x;xx.x	xx.x;xx.x
Min;Max	xx.x;xx.x	xx.x;xx.x	xx.x;xx.x

Shell 101: Summary of rebounds occurring within 2 months after discontinuing open-label phase treatment or relapse treatment: safety analysis set

	LEO 90100 (n=xxx)	Vehicle (n=xxx)
Within 2 months after discontinuation of open-label treatment:		
Number of rebounds	xxx	xxx
Number of subjects	xxx	xxx
Mean (SD)	xx.x (xx.x)	xx.x (xx.x)
Median	xx.x	xx.x
Q1;Q3	xx.x;xx.x	xx.x;xx.x
Min;Max	xx.x;xx.x	xx.x;xx.x
Within 2 months after discontinuation of relapse treatment:		
Number of rebounds	xxx	xxx
Number of subjects	xxx	xxx
Mean (SD)	xx.x (xx.x)	xx.x (xx.x)
Median	xx.x	xx.x
Q1;Q3	xx.x;xx.x	xx.x;xx.x
Min;Max	xx.x;xx.x	xx.x;xx.x

Shell 102: Summary of rebounds occurring within 2 months after discontinuing of maintenance treatment: safety analysis set

	LEO 90100 (n=xxx)	Vehicle (n=xxx)
Within 2 months after discontinuation of maintenance treatment:		
Number of rebounds	xxx	xxx
Number of subjects	xxx	xxx
Mean (SD)	xx.x (xx.x)	xx.x (xx.x)
Median	xx.x	xx.x
Q1;Q3	xx.x;xx.x	xx.x;xx.x
Min;Max	xx.x;xx.x	xx.x;xx.x

Signature Page for TMF-000023733 v1.0

Reason for signing: Approved	Manage Name: PPD Capacit Date of signature: 15-Jul-2019 08:57:51 GMT+0000	(s)
Reason for signing: Approved	Manage Name: PPD Capacit Date of signature: 15-Jul-2019 09:16:48 GMT+0000	dict(s)
Reason for signing: Approved	QC App Name: PPD Capacit Date of signature: 15-Jul-2019 09:20:55 GMT+0000	

Electronic signatures made within eTMF LEO are considered to be a
legally binding equivalent of traditional handwritten signatures.

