6.1.1 Overview

This trial is a multi-centre, prospective trial, consisting of an initial open-label treatment phase of 4 weeks followed by a randomised, double-blind, vehicle-controlled, maintenance phase of 52 weeks in subjects with psoriasis vulgaris.

After the screening phase, subjects deemed eligible for the trial (adults with psoriasis vulgaris on the trunk and/or limbs rated as at least ‘mild’ according to the PGA, BSA 2-30% and m-PASI of at least 2) will be enrolled to the initial open-label phase, where they will apply LEO 90100 once daily on the psoriatic lesions on trunk and/or limbs for 4 weeks.

- Subjects who achieve treatment success (PGA score of ‘clear’ or ‘almost clear’ with at least a 2-grade improvement from baseline) at Week 4 will be randomised in a 1:1 ratio to a maintenance phase of 52 weeks with LEO 90100 or vehicle (maintenance IP) twice weekly.
- Subjects who do not achieve treatment success after 4 weeks of once daily treatment (i.e., non-responders) will be discontinued from the trial.

During the randomised maintenance phase, subjects will apply maintenance IP twice weekly 3 or 4 days apart (fixed days) on all areas on the trunk and limbs where lesions have cleared or almost cleared after the initial open-label phase or after relapse treatment. Subjects will be assessed regularly at clinical visits (every 4 weeks). In addition, if in the opinion of the

subject, a relapse (exacerbation of psoriasis) has occurred between two regular monthly visits, the subject will be assessed by the investigator at an unscheduled visit.

Following confirmation of a relapse the subject will be provided with rescue IP and will be asked to apply it to the active area(s) on trunk and/or limbs, irrespective of whether those areas were active at baseline or they are new lesions. The rescue IP is to be applied once daily on the active areas for 4 weeks. (Note: This treatment is referred to as 'relapse' or 'rescue' treatment). If additional areas become active during rescue treatment, these should also be treated once daily with rescue IP. During a relapse, areas that are not active will continue twice weekly maintenance treatment.

- If a score of 'clear'/'almost clear' according to the PGA is regained after 4 weeks, the twice weekly maintenance regimen will be re-started on the now 'clear'/'almost clear' area(s) according to the original randomisation scheme (for details see section [6.1.4](#)).

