- If a score of 'clear'/'almost clear' according to the PGA is not regained after the 4 weeks of once daily rescue treatment, the subject will exit the trial.

A detailed description of each phase is provided in the section below.

Planned date of enrolment of first subject: Q1-2017

Planned date of completion of last subject: Q3-2019

Estimated number of trial sites and country allocation: Approximately 58 sites in Canada, France, Germany, Poland, United Kingdom and United States.

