5.1 Definition of trial periods

The trial periods are defined in [Table 1](#).

Table 1: Definition of trial periods

Trial period	Definition
Open-label phase	From the day of enrolment to the day before randomisation.
Randomised phase	From the day of randomisation to end of trial, both days included.
Maintenance phase	From the day of first exposure to maintenance IMP to the last day of exposure (rescue or maintenance IMP), both days included.
Follow-up phase	From the day after last application of maintenance or rescue IMP to end of trial.
Relapse period	Relapse is defined as a PGA score of at least 'mild' during the maintenance phase, for details on relapse see CTP section 6.14.1. A relapse period is defined from the relapse start day (included) to the

	visit date when relapse treatment is discontinued (not included).
Remission period	A remission period is a period where the subject is not in a relapse period within the maintenance phase.
Visit interval	The interval between two successive scheduled visits.

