5.5.1 Exposure

Duration of exposure will be summarised as described in the protocol section 11.3.3.1. If the date of last application of IMP is missing, the date of last visit attended by the subject will be used instead.

Patient years of exposure during a trial phase will be calculated as exposure during the relevant phase (accounting for both maintenance and rescue IMP as relevant) divided by 365.25.

The amount of IMP used will be summarised for the open-label treatment phase. For each subject the amount of IMP used will be normalised by the length of the open-label phase.

The total amount of IMP used, and the amount of rescue IMP used will be summarised by treatment group for the maintenance phase. For each subject the total amount of IMP and the amount of IMP used will be normalised by the length of maintenance phase or the total time in relapse, respectively.

The amount of IMP used, and the amount of rescue will not be summarised for each visit interval as described in the protocol. Instead a cumulative plot of the amount of IMP used over time during the maintenance phase by each subject together with an average cumulative amount curve will be done for the safety analysis set. The cumulative amount of IMP for each subject will be normalised by time in the maintenance phase (in days). The cumulative

Trial ID: LP0053-1004	Date: 15-JUL-2019	Version: 1.0 Page 30 of 177
-----------------------	-------------------	--------------------------------

amount of IMP used up to each scheduled visit and the corresponding number of subjects contributing to these amounts will be tabulated by treatment group.

More details for the tables and listings can be found in [Appendix I](#) and [Appendix II](#).

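### SAP 5.5.1 divides rescue product used by time in relapse, but the Shell 92 footnote divides it by days in remission; programmed as written, the shell would misstate daily rescue use.

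*SAP*

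**What the plan says.** SAP 5.5.1 (Exposure) announces two amounts: "The total amount of IMP used, and the amount of rescue IMP used will be summarised by treatment group for the maintenance phase". Within each person, the two amounts "will be normalised by the length of maintenance phase or the total time in relapse, respectively". Total product is therefore divided by the length of the maintenance phase, and rescue product by time in relapse. The normalising sentence omits the word rescue for the second amount, but the order of the preceding sentence makes the meaning clear.

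Shell 92 in Appendix II has a Total IMP and a Rescue IMP column for each arm. Its footnote says the amounts are "normalised by the number of days in the maintenance phase or number of days in remission, respectively". The first denominator agrees with 5.5.1. The second does not.

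SAP Table 1 (section 5.1) settles how the two denominators relate: "A remission period is a period where the subject is not in a relapse period within the maintenance phase". A relapse period runs from the relapse start day up to the visit at which relapse treatment is stopped. Protocol 6.1.1 places rescue use inside that period: "The rescue IP is to be applied once daily on the active areas for 4 weeks".

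Section 5.7 of the SAP, which lists changes from the protocol, does not mention the difference. Nothing in either document says whether SAP text or a shell prevails.

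**The concern.** The two denominators are complements within the maintenance phase. Dividing rescue product by remission days does not give a rate of use over any period in which the product is applied. The result mixes how much is used per relapse day with how much of the time the subject is in relapse, and the latter is what the trial expects to differ between arms.

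Long-term corticosteroid safety is a main aim of the trial (Protocol 3.3.3), so the amount of rescue product matters to readers. Protocol 11.3.3.1 planned rescue amounts by visit interval. SAP 5.5.1 drops those, and the cumulative table and plot that replace them do not separate rescue from maintenance product. The Rescue IMP column of Table 1-38 is then the one planned summary that isolates the amount of rescue product. SAP 5.5.1 sends the reader to the appendices for table details, so a programmer could reasonably follow the footnote.

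**Working it through.** **Inputs.** Vehicle relapse rate r of 4 to 8 per year and hazard ratio 0.7 (Protocol 11.1); rescue course of 4 weeks, or 28 days (Protocol 6.1.1); maintenance phase of 364 days (SAP 5.4.2.1); dropout of 30% over 52 weeks (Protocol 11.1). The documents state no figure for daily rescue use, so let A be grams per relapse day, taken as constant and equal in both arms.

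**Planning figures reproduced.** Mean wait = 52/r weeks: 52/4 = 13.00, 52/6 = 8.67, 52/8 = 6.50, as in Table 16. Median time to dropout = ln 2 / (−ln 0.7 / 52) = 101 weeks, as stated in Protocol 11.1.

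**What each rule prints.**
- Text rule: A × relapse days / relapse days = A.
- Shell rule: A × relapse days / remission days.

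**Pooled size.** Over a cycle of one remission and one rescue course, relapse days / remission days = 4 / mean wait. On active the mean wait is 52/(0.7r): 18.57, 12.38 and 9.29 weeks.

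| Vehicle relapses per year | Vehicle, shell/true | Active, shell/true |
|---|---|---|
| 4 | 4/13.00 = 0.31 | 4/18.57 = 0.22 |
| 6 | 4/8.67 = 0.46 | 4/12.38 = 0.32 |
| 8 | 4/6.50 = 0.62 | 4/9.29 = 0.43 |

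The reciprocals give the understatement: 1.6- to 3.25-fold on vehicle and 2.3- to 4.6-fold on active. The vehicle/active ratio is 1/0.7 = 1.43 in every row, produced by the denominator alone. At a hazard ratio of 1 it is 1.

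For illustration only, take A = 15 g/day (7 cans × 60 g / 28 days, all used; Protocol 10.4). The shell would print about 4.6, 6.9 and 9.2 on vehicle and 3.2, 4.8 and 6.5 on active. The text rule prints 15.0 throughout.

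**Single completer with k courses of 28 days**, shell/true = 28k/(364 − 28k): k = 1 gives 0.083, k = 4 gives 0.44, k = 6 gives 0.86, k = 7 gives 1.17. The direction reverses once relapse days exceed 182.

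**Subject-level simulation.** Shell 92 summarises subject values, so 20,000 subjects per arm were simulated with 30% dropout and an assumed 0, 10 or 20% chance of exit after each course (the documents give no such rate).
- Pooled shell/true: 0.29 to 0.59 on vehicle, 0.20 to 0.41 on active.
- Median among subjects who relapsed: 0.30 to 0.65 on vehicle, 0.19 to 0.44 on active.
- Mean among subjects who relapsed, vehicle at 8 per year: 0.69, 0.93 and 1.18 at 0, 10 and 20% exit. This last case is the only one above 1.
- Subjects who relapsed and are overstated: 1% to 27%.
- Vehicle/active ratio of the means: from 0.63/0.48 = 1.31 to 0.69/0.48 = 1.44.
- Subjects with no relapse: 4% to 16%. The shell rule gives them 0; the text rule gives 0/0.

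**The case against.** The strongest reply is that this is a drafting slip. Section 5.5.1 has the sensible rule, the footnote reads like remission written for relapse, and nobody chose remission days as a method. Shell footnotes elsewhere also lag the text: those of Shells 60, 63 and 66 refer to the maintenance phase and its last 24 weeks, although Appendix I also lists randomised-phase tables with a last period of 32 weeks. This stands as to cause, and it means the wrong rule could be programmed, not that it will be. It does not remove the conflict, because no order of precedence is given.

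The second reply concerns size. The table prints subject-level means, and a subject who relapses early and whose control "is not regained after the 4 weeks of once daily rescue treatment, the subject will exit the trial" has few remission days and a very large ratio. This also stands. A reader might infer that the shell understates every subject and every mean; the simulation shows otherwise.

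Third, a reader might infer that the shell builds in an arm difference whatever the data. It does not: the difference needs relapse frequency to differ between arms. That is the trial's hypothesis (Protocol 3.3.2), but it is not certain.

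Fourth, other information on product use survives: the Total IMP column, cumulative use, active treatment days and the drug accountability listing. None of these summarises rescue amount separately.

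**Conclusion.** The SAP contradicts itself on the denominator for rescue product, and the shell's version is unsuitable for daily use during rescue. At the protocol's planning rates, the pooled value would be about 0.31 to 0.62 of true daily use on vehicle and 0.22 to 0.43 on active, and medians behave similarly. Under a hazard ratio of 0.7, equal true use would appear about 1.4-fold higher on vehicle.

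These figures assume constant and equal daily use, 28-day courses and exponential waits. The ±4-day visit window would change the fractions by about 14% either way (4/28). The behaviour of the means rests on an assumed exit rate.

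Two further readings go too far. The column would not measure relapse frequency alone; it is the product of daily use and the relapse-to-remission ratio. And the trial's conclusions are not at risk: this is one column of a descriptive exposure table, and no primary, secondary or adverse-event analysis uses it.

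**What to change.** Make three small edits before the table is programmed:

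1. In the Shell 92 footnote, replace the word remission with relapse, so that it matches 5.5.1.
2. In the normalising sentence of 5.5.1, insert the word rescue in the second amount.
3. State that the Rescue IMP column includes only subjects with at least one relapse, and show that number in the row for number of subjects. Without this the 5.5.1 rule is undefined for subjects who never relapse.

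The cost is about two lines of wording. No new data are needed and no hypothesis test changes.
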